1. INTRODUCTION

The relationship between type 2 diabetes (T2D) and cancer has gained considerable attention and importance in recent years. These are two highly prevalent conditions in the global population with a significant impact on the healthcare system: in fact, estimates from the International Diabetes Federation (IDF) show that approximately 537 million people suffer from diabetes, the majority of whom have T2D. (1)

The association between the two conditions has been widely studied, revealing how some metabolic processes can be common and influence each other. Hyperglycemia itself, caused by poorly controlled diabetes, can result in the development of a chronic low-grade systemic inflammatory state; this environment arises as a consequence of chronic glucose stimulation of certain mechanisms, including the calcium signal, which leads to the release and increase of inflammatory cytokines and consequent inflammatory cells. (2) Furthermore, in addition to perpetuating the inflammatory state, there is an escalation in ROS (reactive oxygen species) production, triggering oxidative stress and DNA damage, thus advancing cancer development. (3)

Concerning the chronic inflammatory state, it is also crucial to consider the role of obesity, being one of the most important and studied common elements between the two pathologies. In response to hypoxia and oxidative stress, adipose tissue produces high levels of leptin, a pro-inflammatory adipokine. (3, 4) This overproduction can disrupt the equilibrium between leptin and other adipokines, encouraging a state of meta-inflammation that enhances cancer development. It promotes processes such as epithelial-mesenchymal transition (EMT) and cellular adhesion to the extracellular matrix (ECM) (3), while also facilitating cancer immune evasion. (5) It is therefore important to understand how the increase in leptin related to obesity, a risk factor often present in the diabetic population, also plays a significant role in cancer.

Finally, another factor contributing to this inflammatory microenvironment and cytokine production is dyslipidemia, particularly the increase in fatty acids. (3)

Not surprisingly, in addition to these molecules, the microbiota also plays a significant role. Dysbiosis, implicated in various diseases, has been associated with cancer as well, owing to its capacity to influence the genomic stability of host cells and modulate numerous signaling pathways. Consequently, a correlation has been demonstrated between reduced richness of intestinal microbiota and metabolic dysfunctions, including insulin resistance and inflammation. (6)

Another important characteristic of T2D, namely hyperinsulinemia, can also be part of and contribute to the development of cancer. High levels of insulin stimulate not only the insulin receptor but also insulin-like growth factor (IGF-1) (4), which is implicated in the onset and development of various types of cancers. Studies on murine models have shown how the administration of IGF-1 not only promotes the proliferation of cancer cells but also their ability to metastasize. (7)

In addition to this hormone, mTOR is also a central molecule, which regulates processes such as growth and metabolism, (8) thus potentially playing a role in both pathologies. Dysregulations of metabolism with increased nutrient intake, as in the majority of patients with T2D, lead to hyperactivation and stimulation of this signal, which contributes to the worsening of diabetic pathology with increased insulin secretion. (9)

The same signal can activate various mechanisms, including the MAP kinase pathway, which is frequently subject to mutations in some types of cancers. Furthermore, hyperactivation of the mTOR pathway contributes to the promotion of pro-oncogenic proteins, which control fundamental processes for the survival of cancer cells, such as angiogenesis, metabolism, and the capacity for metastatic spread. (10)

An interesting metabolic phenomenon is the Warburg effect, which explains how, despite ample oxygen availability, cancer cells prefer to generate energy through glycolysis, which requires increased glucose uptake, making the hyperglycemic environment advantageous for cancer cells. Moreover, this process leads to increased production of a precursor of advanced glycation end products (AGEs), which means that the Warburg effect not only affects the metabolism of cancer cells but also contributes to the development of diseases by promoting the accumulation of AGEs. (3)

Finally, even diabetes drugs could be implicated. One extensively studied drug is metformin, which has shown potential as an antineoplastic agent in diabetic subjects, unlike exogenous insulin, which seems to act as a growth factor potentially implicated in cancer proliferation. (11)

All these common metabolic processes, as well as others, highlight the importance of carefully characterizing the population of diabetic patients also affected by cancer in order to understand the associated risk factors. As cancer represents a complication of diabetes, this study underscores the primary objective, which is to emphasize the necessity for tailored prevention strategies in clinical settings. These strategies aim to address specific diabetes-related risk factors that potentially contribute to cancer onset.

2. OBJECTIVES

The primary objective of the study is to identify risk factors for cancer onset in the population affected by T2D.

Secondary objectives include:

1. Description of demographic, clinical, and first-line therapy characteristics of patients at the diagnosis of T2D.
2. Evaluation of risk factors for recurrence, presence of a second cancer unrelated to the first, and presence of both events in patients who have had cancer.
3. Investigating the correlation between patient characteristics and time to cancer onset.

3. MATERIALS AND METHODS

3.1 Study Design

The study follows a retrospective, monocentric cohort design, utilizing data sourced from the Smart Digital Clinic electronic medical record (Meteda Srl).

3.3 Subjects

All patients visited at the Endocrinology and Diabetology Outpatient Clinic of the AOU Maggiore della Carità in Novara for a first diagnosis of T2D between 1990 and 2010 will be included in the study.

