3.6 Follow-up and Events of Interest

Patients included in the study will be followed from the date of diagnosis of T2D until the date of the last available visit.

During the follow-up, for all included patients, the year of onset of the first cancer occurring after the diagnosis of diabetes and the type of cancer will be recorded. From this information, it will be possible to calculate the time elapsed between the diagnosis of diabetes and the onset of the tumor (measured in years).

For patients who have developed cancer, the following will also be recorded:

- Cancer recurrence (year of recurrence onset)
- Diagnosis of a second cancer unrelated to the primary cancer (year of onset, type of cancer)

Cancer diagnosis will be identified through the extraction system from the Smart Digital Clinic electronic medical record (Meteda Srl), using relevant keywords in the cancer domain, identified in the medical history section. The keywords will include: metastasis, adenocarcinoma, carcinoma, neoplasm, secondary, sarcoma, cancer, adenoma, lymphoma, leukemia, glioma, glioblastoma, basal cell carcinoma, squamous cell carcinoma, melanoma, mesothelioma, chordoma, anaplastic, differentiated, undifferentiated, meningioma, multiple myeloma, small cell carcinoma, thymoma, craniopharyngioma, neuroendocrine, LH, NHL, K, GIST, HCC, and NET.

SCDU di Endocrinologia

AOU Maggiore della Carità, [name]
[contact] (Reparto); [contact]
[contact]

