3.7 Data Collection

For each patient, the following variables will be extracted from the Smart Digital Clinic electronic medical record extraction system, when possible:

- Gender and age;
- Smoking habit and alcohol consumption (units per day);
- Weight and body mass index (BMI) at the first (T0) and last visit (T1);
- Date of diagnosis of T2D;
- Date of the first visit;
- Treatment for T2D at T0 and T1;
- Levels of glycated hemoglobin (HbA1c) at T0 and T1, average HbA1c, and average fasting blood glucose;
- Creatinine clearance at T0 and T1;
- Liver enzymes at T0 and T1: alanine aminotransferase (ALT) and aspartate aminotransferase (AST);
- Lipid profile at T0 and T1: low-density lipoprotein (LDL-c) and triglycerides (TG);
- Complications of T2D;
- Treatment for the cancer;
- Family history of cancers.

The diagnosis of T2D is confirmed at diabetic centers or, in some cases, by general practitioners who refer patients to specialized diabetic centers. The accuracy of the diagnosis will be confirmed by cross-referencing with the Piedmont Diabetic Registry (PDR) and involving a second person to ensure precise assessment.

Glycated hemoglobin will be considered high if its values exceed or equal 8%, indicating glycemic decompensation, while it will be considered low if it presents values below 8%.

BMI categories will be divided into underweight (BMI <18.5 kg/m²), normal weight (BMI 18.5 – 25 kg/m²), and overweight (BMI >25 kg/m²).

Regarding the treatment of T2D, participants will be categorized and grouped for statistical purposes into the following classes:

- Dietary therapy;
- Metformin/Acarbose;
- Sulfonylurea;
- Metformin + GLP1/DPP4 inhibitors (DPP4i) or only GLP1 or only DPP4i;
- Metformin + SGLT2 inhibitors (SGLT2i) or only SGLT2i;
- Basal insulin + GLP1/DPP4i +/- Metformin;
- Basal insulin +/- Metformin +/- SGLT2i;
- Basal bolus insulin;
- Basal bolus insulin +/- Metformin +/- SGLT2i.

Furthermore, complications of metabolic pathology will be extracted from the dedicated section of the program, where they are systematically recorded and organized, and their diagnosis is conducted in accordance with appropriate guidelines. These complications will be divided into the following categories: vasculopathy, neuropathy, hypertension, heart disease, renal failure, and retinopathy.

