3.9 Statistical Analysis

Descriptive statistics will be calculated to summarize patient information.

Categorical variables will be reported as absolute frequencies and percentages, while numerical variables will be reported as mean and standard deviation or median (Q1-Q3) if not distributed according to a normal random variable according to the Shapiro-Wilk test and observation of the QQ plot.

SCDU di Endocrinologia

AOU Maggiore della Carità, [name]
[contact] (Reparto); [contact]
[contact]

Univariate and multivariate Cox proportional hazards regression models will be used to estimate hazard ratios (HRs) and corresponding 95% confidence intervals (95% CI) for the association between some risk factors, including particularly glycemic level, and cancer onset. The stepwise method will be used to select variables to include in the model. For this analysis, time to event will be calculated as the number of years between cancer onset and diabetes diagnosis for subjects who develop the cancer, and as the number of years between the last available visit and the date of diabetes diagnosis. The possibility of conducting an analysis separately for cancer type or considering specific cancer types based on the number of observed events will be evaluated. The same models will be used to estimate the association with the risk of recurrence, second cancer, or both in patients who have developed cancer. In this case, time to event will be calculated considering the difference in years between recurrence onset, second cancer, or last visit and the onset of the first cancer.

Linear regression models will be used to evaluate the relationship between variables measured at diagnosis and time to cancer onset. In case the assumptions of the linear model are not met (normality of residuals and homoscedasticity), the Spearman correlation coefficient will be calculated to measure the correlation between numerical variables and time to tumor onset, while the Mann-Whitney or Kruskall-Wallis tests will be used when variables measured at baseline are categorical.

The significance level will be set at 0.05, and all tests performed will be two-tailed. Finally, the analyses will be conducted using SAS software (version 9.4; SAS Institute, Cary, NC, USA).

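### Diagnoses from 1990 to 2010 share one baseline hazard with no stated calendar term, so a joint drift in risk factors and recorded cancer would bias the hazard ratios by an unknown amount

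*Combined protocol and SAP*

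**What the plan says.** Section 3.3 defines the cohort as all patients seen at the clinic "for a first diagnosis of T2D between 1990 and 2010 will be included in the study". Section 3.6 sets the observation period: "Patients included in the study will be followed from the date of diagnosis of T2D until the date of the last available visit".

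Section 3.9 puts the Cox models on the same clock: "time to event will be calculated as the number of years between cancer onset and diabetes diagnosis for subjects who develop the cancer". Patients without cancer are censored at the last visit. Covariates are chosen by an automatic rule: "The stepwise method will be used to select variables to include in the model". The section does not list the candidate variables and forces none into the model. It names no stratification, no calendar-period or diagnosis-year term, and no sensitivity analysis by era.

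Section 3.7 lists "Date of diagnosis of T2D" among the extracted variables, so the information is in hand. The only role section 3.9 states for it is in computing time to event. Section 3.7 also collects "Treatment for T2D at T0 and T1", with one list of treatment classes for both visits.

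**The concern.** On a years-since-diagnosis clock, patients at the same follow-up time can be in very different calendar years. Five years after diagnosis, a patient diagnosed in 1990 is in 1995 and one diagnosed in 2010 is in 2015, yet the model gives both the same baseline hazard. If recorded cancer incidence differs between those years, through detection or through what is written in the record that section 3.6 searches by keyword, the difference goes to any covariate whose distribution also moved with diagnosis year.

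The primary objective is to identify risk factors for cancer onset, and section 3.9 singles out glycaemic level. The design effect is an HR of 1.2, so a modest calendar bias could hide or imitate a good part of it. Adjusting for age does not remove the problem, since two patients of the same age can be diagnosed 20 years apart. The univariate models have no adjustment at all.

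**Working it through.** **Inputs.** The plan has no figure for a calendar effect, so there is none to reproduce. From the plan: the 1990-2010 window (3.3), 13% prevalence of high HbA1c and a design HR of 1.2 (3.8). The 779 events in 3.8 do not follow from its inputs: the Schoenfeld formula gives 2,088, or 2,320 if the stated correlation is read as R² = 0.1. That is a separate matter, and this point does not depend on it.

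**Assumptions.** Two eras with equal person-time, no true effect of the exposure, exposure prevalence pE (earlier) and pL (later), and recorded cancer incidence h times as high in the later era.

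**Formula.** Apparent HR = [(pE + pL·h)/(pE + pL)] ÷ [((1−pE) + (1−pL)·h)/((1−pE) + (1−pL))].

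**HbA1c, mean prevalence 13%.**

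| pE | pL | h | Exposed | Unexposed | Apparent HR |
|---|---|---|---|---|---|
| 18% | 8% | 1.2 | 0.276/0.26 = 1.062 | 1.924/1.74 = 1.106 | 0.96 |
| 18% | 8% | 1.5 | 0.300/0.26 = 1.154 | 2.200/1.74 = 1.264 | 0.91 |
| 20% | 6% | 1.5 | 0.290/0.26 = 1.115 | 2.210/1.74 = 1.270 | 0.88 |
| 8% | 18% | 1.5 | 0.350/0.26 = 1.346 | 2.150/1.74 = 1.236 | 1.09 |

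The range 0.88 to 1.09 describes these four cases and is not a bound. For example, 6% rising to 20% with h = 1.5 gives (0.36/0.26) ÷ (2.14/1.74) = 1.13. If pE = pL or h = 1, the ratio is exactly 1.

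**Treatment class used only in the later era, against all other patients.** With pE = 0, the formula becomes h ÷ [(1 + (1−pL)·h)/(2−pL)]. With h = 1.5:
- pL near 0: 1.5/1.25 = 1.20
- pL = 20%: 1.5/(2.2/1.8) = 1.23
- pL = 40%: 1.5/(1.9/1.6) = 1.26
- pL = 100%: 1.5/1 = 1.50

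**Cox simulation.** The formula ignores the shorter potential follow-up of later patients, so a simulation with no HbA1c effect was also run: 4,000 patients, diagnosis spread over the window, closing year 2024 and random loss to follow-up (all assumed), about 630 to 670 events, 40 replicates per scenario.

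| Hazard per 10 years | Odds of high HbA1c per 10 years | HR, no calendar term | HR, year adjusted | HR, period strata |
|---|---|---|---|---|
| ×1 | ×0.5 | 0.98 | 0.98 | 0.98 |
| ×1.5 | ×1 | 1.00 | 0.99 | 0.99 |
| ×1.25 | ×0.6 | 0.97 | 1.00 | 1.00 |
| ×1.5 | ×0.6 | 0.94 | 1.00 | 0.99 |
| ×1.5 | ×0.4 | 0.90 | 1.00 | 1.00 |
| ×2 | ×0.4 | 0.82 | 0.99 | 0.97 |
| ×0.67 | ×0.4 | 1.12 | 1.00 | 1.01 |

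Monte Carlo error is about 0.02 on the log scale: 1/√(640 × 0.13 × 0.87) = 0.12 per replicate, divided by √40. The first two rows, with only one trend, show no bias beyond it.

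**Cost of adjustment for HbA1c.** R² between era and high HbA1c is ((pE−pL)/2)²/(0.13 × 0.87). For 16%/10% it is 0.008 and for 20%/6% it is 0.043. Dividing by 1 − R² raises the required events by about 1% to 4.5%, for example from 779 to between 786 and 815.

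**The case against.** The strongest reply is that both trends are assumed. Bias needs a calendar trend in the exposure and another in recorded cancer incidence, and the documents report neither. Section 3.6 describes one keyword search applied to every patient. This stands: the point is a gap in the model, not a bias shown to be present.

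The shifts are also modest against sampling error. With the planned 779 events and 13% prevalence, the standard error of the log HR is 1/√(779 × 0.13 × 0.87) = 0.107, so HR 0.96 is about 0.4 and HR 0.91 about 0.9 standard errors from the null. That is fair. But ln 0.91 is half the size of ln 1.2 (0.092 against 0.182), and a systematic shift does not shrink as events accrue.

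Stepwise selection might pick up diagnosis year. The plan does not exclude it, but neither names it as a candidate nor forces it in, so its use is unspecified. The plan also does not say whether first-visit, last-visit or average HbA1c enters the model. The scenarios apply to whichever is used, provided that it drifts.

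A reader might infer that treatment at the first visit depends on era because the class list runs from diet to SGLT2 inhibitors. The documents do not support this: the list serves both visits, and nothing says when any class came into use. Nor does it follow that 1990 and 2010 patients are compared throughout follow-up. Follow-up ends at the last visit, so late risk sets hold mainly earlier-diagnosed patients. The simulation allows for this and still shows the bias.

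**Conclusion.** The concern holds as a low-cost safeguard against a bias of unknown size and direction. The structural gap is plain from the text: a 20-year diagnosis window, one baseline hazard, no stated calendar term, and the diagnosis date already collected.

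Under the four two-era scenarios, a null HbA1c effect appears as HR 0.88 to 1.09. Three of the four fall below 1, so masking a harmful association is as much a risk as creating a false one. A treatment class used only in the later era, by 40% or fewer, would show about 1.2 to 1.3 at a 1.5-fold incidence difference.

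Two stronger readings should be resisted. One is that era will be reported as a patient risk factor; that would need evidence of both trends. The other is that a class confined to one era absorbs the whole 1.5-fold difference. Later-era patients not on the class share the higher incidence, so against all other patients the ratio reaches 1.5 only if every later-era patient uses it.

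**What to change.** In section 3.9, state that every cancer-onset Cox model, univariate and multivariate, includes calendar period of T2D diagnosis, exempt from stepwise selection. Two forms serve:
- strata of the baseline hazard, for example four periods of roughly five years (1990-94, 1995-99, 2000-04, 2005-10); or
- diagnosis year as a forced covariate.

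Both brought the simulated null HR back to about 0.97 to 1.01. Strata make no assumption about the shape of the trend between periods; the covariate avoids choosing cut-points, which the documents do not supply. Either should be fixed before the data are examined.

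No new data are needed: one sentence in 3.9 and one added statement or term in the SAS code. The precision loss for HbA1c is small, about 1% to 4.5% more events under the assumed trends. It is larger for any treatment class closely tied to one period, because little within-period contrast remains. With strata, no separate rule on reporting treatment HRs by period is needed, since a stratum in which nobody uses a class adds nothing to that class's HR.

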3.3.1 Inclusion Criteria

- Adult age
- Diagnosis of T2D

SCDU di Endocrinologia

AOU Maggiore della Carità, [name]
[contact] (Reparto); [contact]
[contact]

3.3.2 Exclusion Criteria

- Diagnosis of tumor before the diagnosis of T2D
- Diagnosis of secondary diabetes due to other pathologies
- Diagnosis of secondary diabetes due to other medications
- Diagnosis of secondary diabetes due to surgical interventions

3.4 Intervention

No intervention of any kind.

3.5 Study Duration

24 months.

3.6 Follow-up and Events of Interest

Patients included in the study will be followed from the date of diagnosis of T2D until the date of the last available visit.

During the follow-up, for all included patients, the year of onset of the first cancer occurring after the diagnosis of diabetes and the type of cancer will be recorded. From this information, it will be possible to calculate the time elapsed between the diagnosis of diabetes and the onset of the tumor (measured in years).

For patients who have developed cancer, the following will also be recorded:

- Cancer recurrence (year of recurrence onset)
- Diagnosis of a second cancer unrelated to the primary cancer (year of onset, type of cancer)

Cancer diagnosis will be identified through the extraction system from the Smart Digital Clinic electronic medical record (Meteda Srl), using relevant keywords in the cancer domain, identified in the medical history section. The keywords will include: metastasis, adenocarcinoma, carcinoma, neoplasm, secondary, sarcoma, cancer, adenoma, lymphoma, leukemia, glioma, glioblastoma, basal cell carcinoma, squamous cell carcinoma, melanoma, mesothelioma, chordoma, anaplastic, differentiated, undifferentiated, meningioma, multiple myeloma, small cell carcinoma, thymoma, craniopharyngioma, neuroendocrine, LH, NHL, K, GIST, HCC, and NET.

SCDU di Endocrinologia

AOU Maggiore della Carità, [name]
[contact] (Reparto); [contact]
[contact]

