Finally, regarding cancer, treatment will be categorized into three classes: chemotherapy, surgery, and radiotherapy. Additionally, cancer types will be divided to ensure greater homogeneity among groups, including the nervous system, head and neck, thorax, gastrointestinal, gynecological, urinary tract, male genital system, skin, blood, breast, soft tissues, endocrine glands, and neuroendocrine cancers.

Such information will be collected at the diabetes diagnosis visit and the last visit before cancer onset for subjects experiencing the event, and at the last available visit for the remaining subjects.

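### The Cox clock starts at T2D diagnosis, but patients enter the cohort at the clinic; where the two dates differ, the plan needs delayed entry and a rule for cancers in between

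*Combined protocol and SAP*

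**What the plan says.** **Clock.** Section 3.6: "Patients included in the study will be followed from the date of diagnosis of T2D until the date of the last available visit". Section 3.9 repeats this for the Cox model. For cases, "time to event will be calculated as the number of years between cancer onset and diabetes diagnosis for subjects who develop the cancer"; for the others, time runs "as the number of years between the last available visit and the date of diabetes diagnosis".

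**Entry.** Section 3.3 includes patients seen at this outpatient clinic for a first diagnosis of T2D between 1990 and 2010. Section 3.7 says that the diagnosis is confirmed at diabetic centres or "in some cases, by general practitioners who refer patients to specialized diabetic centers".

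**Baseline.** The list in section 3.7 makes T0 the first visit: "Weight and body mass index (BMI) at the first (T0) and last visit (T1"). The end of the same section says "Such information will be collected at the diabetes diagnosis visit and the last visit before cancer onset for subjects experiencing the event". The list has the date of T2D diagnosis and, as a separate item, "Date of the first visit". Section 3.9 never uses the first-visit date: it has no delayed entry, landmark or related sensitivity analysis.

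**Events.** Section 3.3.2 excludes tumours before T2D diagnosis, not tumours before the first visit. Section 3.6 counts the first cancer after T2D diagnosis, finds it by keyword search of the medical history, and records onset by year.

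**The concern.** A patient diagnosed elsewhere comes under observation only on reaching this clinic. If that is later than the diagnosis, the interval is left-truncated: anyone who died of cancer in it, or was never referred because of it, is not in the cohort. The Cox rule as written still counts the interval as fully observed time at risk.

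Gap cancers that do get into the record raise a second problem. They qualify as events, but HbA1c, BMI and treatment at T0 were then measured after the cancer, and the illness or its treatment may have changed them. Section 3.7 asks for data at the last visit before cancer onset; for these patients no such clinic visit exists. The plan has no rule for them.

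The main exposure is HbA1c (high means 8% or more). If time to referral is related to HbA1c, unobserved time is credited unequally to the two groups and the HR is distorted. Section 3.8 targets an HR of only 1.2, so modest distortion matters.

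**Working it through.** The plan gives no figure for the gap, so there is nothing of its own to reproduce. What follows is a range by assumption.

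**From the documents (3.8):** true HR 1.20; 13% with high HbA1c.

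**Assumed:** cancer hazard 1% per year; exponential gaps between diagnosis and first visit, with mean g_L in the low and g_H in the high HbA1c group; follow-up after the first visit uniform on 5 to 20 years, mean F = (5 + 20)/2 = 12.5; a share c of gap cancers captured from the history, with all other gap cancers absent from the cohort.

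**Hand approximation.** In a group with mean gap g, events are proportional to F + c·g, while the time counted is F + g. The apparent rate is therefore the true rate times (F + c·g)/(F + g), and

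HR from diagnosis ≈ 1.20 × [(F + c·g_H)/(F + g_H)] ÷ [(F + c·g_L)/(F + g_L)].

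- If c = 1, both factors are 1 and the HR is 1.20 whatever the gaps.
- If g_L = g_H, the factors cancel and the HR is again 1.20. With nothing captured, absolute rates are still diluted: with a 1-year gap, by 12.5/13.5 = 0.93.
- 1 vs 2 years, c = 0: 1.20 × (12.5/14.5) ÷ (12.5/13.5) = 1.20 × 0.862 ÷ 0.926 = 1.12.
- 1 vs 2 years, c = 0.5: 1.20 × (13.5/14.5) ÷ (13.0/13.5) = 1.20 × 0.931 ÷ 0.963 = 1.16.

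**Simulation.** Cox models on the same assumptions (200,000 patients, 10 replicates per scenario, Monte Carlo standard error of the log HR at most about 0.007):

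| Mean gap, low / high HbA1c (years) | No capture | Half captured | Full capture |
|---|---|---|---|
| 1 / 1 or 3 / 3 | 1.20 | 1.20 | 1.20 |
| 1 / 2 | 1.11 | 1.16 | 1.20 |
| 1 / 3 | 1.03 | 1.12 | 1.20 |
| 2 / 1 | 1.31 | 1.25 | 1.20 |

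Equal-gap and full-capture entries are 1.20 within simulation error. With patients entering the risk set at the first visit and gap cancers left out, the HR was 1.19 to 1.22 in every scenario.

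**Against the target.** The excess hazard sought is 0.20. With 1 vs 2 years, the loss is 0.09 with no capture (nearly half of it) and 0.04 with half captured (a fifth). With 2 vs 1 years, the HR is overstated by 0.11 and 0.05.

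**The case against.** The strongest reply is that the two dates may rarely differ. Section 3.3 speaks of patients seen for a first diagnosis of T2D, section 3.7 puts baseline at the diagnosis visit, and general-practitioner diagnosis applies only in some cases. Extracting two dates does not prove that they differ. This stands as a limit on size: a reader might infer that patients in general enter late, and the documents do not show that. It does not remove the point, because section 3.7 also describes diagnosis followed by referral and defines T0 as the first visit.

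A second reply is that gap cancers can be seen. A reader might infer that the gap is guaranteed free of observed cancer. It is not: sections 3.3.2 and 3.6 let a cancer after diagnosis but before the first visit be found in the history and counted. What is guaranteed is only that the patient reached the clinic. With full capture the HR bias disappears, but the problem of covariates measured after the event remains.

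Third, nothing in the documents links referral delay to HbA1c, and the direction of any bias is unknown. That is correct, and it is why the figures are conditional. Onset by year also means that gaps of less than a year are at or below the resolution of the data.

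Finally, leaving gap cancers out of the primary model discards events. That is a real cost, and it is the reason to keep them in a sensitivity analysis.

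**Conclusion.** The point holds in a conditional form. As written, the Cox rule counts time before clinic entry as at risk for any patient with a gap, and it can relate a cancer to covariates measured after it. Section 3.7 also gives two descriptions of baseline, which need reconciling whatever the size of the bias.

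The HR for HbA1c is materially biased only if gaps differ by HbA1c level and capture of gap cancers is incomplete. The plan assures neither equal gaps nor full capture. In the scenarios examined, a true HR of 1.20 is estimated at between 1.03 and 1.31 with no capture, and between 1.12 and 1.25 with half captured. A reader might infer a bias as large as the effect sought. That needs almost no capture together with about a threefold difference in gap, and the documents support neither assumption. The hazard, the gap distributions, the follow-up and the capture share are all assumed.

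**What to change.** In sections 3.6, 3.7 and 3.9:

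1. Define T0 once, and align the variable list in 3.7 with that section's closing paragraph.
2. Keep time since T2D diagnosis as the time scale, but enter each patient into the risk set at the first-visit date (delayed entry; in SAS PHREG, the ENTRY= option or start-stop input).
3. Leave cancers before the first visit out of the primary model, because their T0 covariates follow the event.
4. Since onset is recorded by year, state how a cancer in the same calendar year as the first visit is ordered.
5. Report the distribution of the gap by HbA1c group, with the number of gap cancers found.
6. Give the from-diagnosis analysis, including captured gap cancers, as a sensitivity analysis.

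The cost is one model option using two dates already on the extraction list. Where the dates coincide, nothing changes. Some events and person-time are lost: under the assumptions above, if every patient had a mean gap of 1 year and all gap cancers were captured, about 1/13.5 = 7.4% of cancers would leave the primary model, or 58 of the planned 779. The loss is smaller if only some patients have a gap, and larger if gaps are longer.
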